EORTC	European Organisation for Research and Treatment of Cancer
ЕОТ	end of treatment
ESMO	European Society for Medical Oncology
EZH2	enhancer of zeste homolog 2
FACS	fluorescence-activated cell sorting
FAS	full analysis set
FDA	Food and Drug Administration
FDG	fluorodeoxyglucose
FL	follicular lymphoma
FLIPI	Follicular Lymphoma International Prognostic Index
FSH	follicle-stimulating hormone
GCP	Good Clinical Practice
G-CSF	granulocyte colony-stimulating factor
GDPR	General Data Protection Regulation
GELF	Groupe d'Etude des Lymphomes Folliculaires
GGT	gamma-glutamyl transferase
HBcAb	hepatitis B core antibody
HBsAb	hepatitis B surface antibody
HBsAg	hepatitis B surface antigen
HBV	hepatitis B virus
HCV	hepatitis C virus

Abbreviations and Special Terms	Definition
HIPAA	Health Insurance Portability and Accountability Act of 1996
HIV	human immunodeficiency virus
HR	hazard ratio
IB	Investigator's Brochure
ICF	informed consent form
ICH	International Council for Harmonisation of Technical Requirements for Pharmaceuticals for Human Use
IDMC	independent data monitoring committee
IEC	independent ethics committee
IgA	immunoglobulin A
IgG	immunoglobulin G
IgM	immunoglobulin M
IMP	investigational medicinal product
INV	investigator
IRB	institutional review board
IRC	independent review committee
IRR	infusion-related reaction
IRT	interactive response technology
IV	intravenous
J-GCP	Japanese Good Clinical Practice
JPI	Japanese package insert
LiHep	lithium heparin
LVEF	left-ventricular ejection fraction
mAb	monoclonal antibody
MCL	mantle cell lymphoma
MedDRA	Medical Dictionary for Regulatory Activities
MOA	mechanism of action
MRD	minimal residual disease
MRI	magnetic resonance imaging
MUGA	multigated acquisition
MZL	marginal zone lymphoma
NA	not applicable
NCCN	National Comprehensive Cancer Network
NCI	National Cancer Institute

Abbreviations and Special Terms	Definition
NE	not evaluable
NHL	non-Hodgkin lymphoma
NK	natural killer
NKCC	natural killer cell count
NR	not reached
ORR	overall response rate
OS	overall survival
PCR	polymerase chain reaction
PD	progressive disease
PET	positron emission tomography
PFS	progression-free survival
PHL	potential Hy's law
PI3K	phosphatidylinositol 3-kinase
PK	pharmacokinetics
PMDA	Pharmaceuticals and Medical Devices Agency
PML	progressive multifocal leukoencephalopathy
POD24	progression of disease within 24 months after initial diagnosis
PP	per protocol
PPS	per protocol set
PR	partial response
PT	prothrombin time
QD	once daily
QoL	quality of life
\mathbb{R}^2	rituximab + lenalidomide (Revlimid®)
R-CHOP	rituximab, cyclophosphamide, doxorubicin, vincristine, and prednisone/prednisolone
R ² -CHOP	rituximab, lenalidomide, cyclophosphamide, doxorubicin, vincristine, and prednisone/prednisolone
RNA	ribonucleic acid
R/R	relapsed/refractory
RSI	Reference Safety Information
SAE	serious adverse event
SAF	safety analysis set
SAP	Statistical Analysis Plan

Abbreviations and Special Terms	Definition
SARS-CoV-2	severe acute respiratory syndrome coronavirus 2
SD	stable disease
SLL	small lymphocytic lymphoma
SmPC	Summary of Product Characteristics
SoA	schedule of activities
SOC	system organ class
SOP	standard operating procedure
SPM	second primary malignancy
Study drugs	Study drugs are defined as tafasitamab/matching placebo, lenalidomide, and rituximab; tafasitamab, lenalidomide, and rituximab are regarded as IMPs (see Table 7 for the exceptions).
Study treatment	Study treatment is defined as tafasitamab plus lenalidomide in addition to rituximab (Treatment Group A [TGA]) or tafasitamab placebo plus lenalidomide in addition to rituximab (Treatment Group B [TGB]).
SUSAR	suspected unexpected serious adverse reaction
TEAE	treatment-emergent adverse event
TEAE TGA	treatment-emergent adverse event Treatment Group A
TGA	Treatment Group A
TGA TGB	Treatment Group A Treatment Group B
TGA TGB TLS	Treatment Group A Treatment Group B tumor lysis syndrome
TGA TGB TLS TSH	Treatment Group A Treatment Group B tumor lysis syndrome thyroid-stimulating hormone
TGA TGB TLS TSH	Treatment Group A Treatment Group B tumor lysis syndrome thyroid-stimulating hormone
TGA TGB TLS TSH TT	Treatment Group A Treatment Group B tumor lysis syndrome thyroid-stimulating hormone thrombin time
TGA TGB TLS TSH TT	Treatment Group A Treatment Group B tumor lysis syndrome thyroid-stimulating hormone thrombin time upper limit of normal
TGA TGB TLS TSH TT ULN USPI	Treatment Group A Treatment Group B tumor lysis syndrome thyroid-stimulating hormone thrombin time upper limit of normal United States prescribing information
TGA TGB TLS TSH TT ULN USPI VHP	Treatment Group A Treatment Group B tumor lysis syndrome thyroid-stimulating hormone thrombin time upper limit of normal United States prescribing information Voluntary Harmonisation Procedure
TGA TGB TLS TSH TT ULN USPI VHP VTE	Treatment Group A Treatment Group B tumor lysis syndrome thyroid-stimulating hormone thrombin time upper limit of normal United States prescribing information Voluntary Harmonisation Procedure venous thromboembolism
TGA TGB TLS TSH TT ULN USPI VHP VTE WBC	Treatment Group A Treatment Group B tumor lysis syndrome thyroid-stimulating hormone thrombin time upper limit of normal United States prescribing information Voluntary Harmonisation Procedure venous thromboembolism white blood cell

1. PROTOCOL SUMMARY

This Phase 3 double-blind, placebo-controlled, randomized study is designed to investigate whether tafasitamab and lenalidomide as an add-on to rituximab provides improved clinical benefit compared with lenalidomide as an add-on to rituximab alone in patients with R/R FL Grade 1 to 3a or R/R MZL.

Protocol Title:

A Phase 3, Randomized, Double-Blind, Placebo-Controlled, Multicenter Study to Evaluate the Efficacy and Safety of Tafasitamab Plus Lenalidomide in Addition to Rituximab Versus Lenalidomide in Addition to Rituximab in Patients With Relapsed/Refractory (R/R) Follicular Lymphoma Grade 1 to 3a or R/R Marginal Zone Lymphoma

Protocol Number: INCMOR 0208-301

Objectives and Endpoints:

Table 1 presents the primary and major/key secondary objectives and endpoints.

Table 1: Primary and Major/Key Secondary Objectives and Endpoints

Objectives	Endpoints
Primary	
To compare the efficacy of tafasitamab and lenalidomide in addition to rituximab to the efficacy of placebo and lenalidomide in addition to rituximab in terms of PFS in participants with R/R FL.	PFS by INV assessment in the FL population, using the Lugano 2014 criteria (Cheson et al 2014). PFS is defined as the time from randomization to first documented disease progression, or death from any cause, whichever occurs first.
Key Secondary	
To compare the efficacy of tafasitamab and lenalidomide in addition to rituximab versus placebo and lenalidomide in addition to rituximab in terms of PFS in the overall population (FL and MZL).	PFS by INV assessment in the overall population (FL and MZL populations).
To compare the efficacy of tafasitamab and lenalidomide in addition to rituximab versus placebo and lenalidomide in addition to rituximab in terms of PET-CR rate in FDG-avid FL participants and OS in the FL population.	 PET-CR rate by INV in the FDG-avid FL population, defined as a complete metabolic response at any time after start of treatment. OS in the FL population.

Overall Design:

Table 2 presents the key study design elements. Further study details are presented after the table.

Table 2: Key Study Design Elements

Study Phase	Phase 3
Clinical Indication	Participants with an investigator-assessed diagnosis of R/R FL Grade 1, 2, or 3a or R/R MZL who have been previously treated with at least 1 anti-CD20 antibody containing therapy (eg, rituximab, obinutuzumab, or other).
Population	Male and female participants at least 18 years of age who have histologically confirmed Grade 1, 2 or 3a FL or histologically confirmed nodal MZL, splenic MZL, or extranodal MZL.
	• Must have been previously treated with at least 1 prior systemic anti-CD20 immunotherapy or chemo-immunotherapy. This includes treatments such as rituximab monotherapy or chemotherapy plus immunotherapy with rituximab or obinutuzumab, with or without maintenance.
	 Must have documented relapsed, refractory, or PD after treatment with systemic therapy:
	 Relapsed lymphoma: relapsed after initial response of CR or PR ≥ 6 months after prior therapy.
	 Refractory lymphoma: achieved less than PR to the last treatment or achieved a CR or PR that lasted less than 6 months.
	 Progressive lymphoma: PD after initial response of SD to prior therapy.
Number of Participants	A total number of 174 PFS events in the FL population are required to detect a HR of 0.65 with 80% power for the primary analysis, using a 2-sided log-rank test at an alpha level of 5% and a 1:1 randomization ratio between the 2 treatment groups. A total of 528 participants with R/R FL need to be randomized 1:1 with stratification (264 participants per treatment group), assuming a median PFS of 27.8 months for lenalidomide in addition to rituximab, 21 months of enrollment, 12 months of follow-up for PFS and 15% of dropouts.
	A minimum of 60 and up to 90 additional participants with R/R MZL will be randomized at a 1:1 ratio to 1 of the 2 treatment groups. The number of participants with MZL is based on an expected enrollment proportion of FL and MZL participants.
	Approximately 275 centers globally (Europe, Asia Pacific, North America) will be participating in this study.

Table 2: Key Study Design Elements (Continued)

Study Design

This Phase 3, multicenter, randomized, double-blind, placebo-controlled study is designed to evaluate the efficacy and safety of tafasitamab and lenalidomide in addition to rituximab versus placebo and lenalidomide in addition to rituximab in participants with R/R FL or MZL.

Approximately 618 participants will be randomized, including approximately 528 participants with FL and 60 to 90 participants with MZL. Participants will be randomized 1:1 to 1 of 2 treatment groups.

An IDMC will review the safety data after the first 60 participants (approximately 30 in each treatment group) have completed 2 cycles of study treatment to monitor and evaluate the safety of the combination treatment.

An interim analysis for futility will be performed at approximately 20% information rate (35 PFS events approximately) in the FL population (an HR of \geq 1.05 will be considered as a nonbinding futility boundary). An IDMC will be involved in reviewing the interim analysis and provide their recommendation as defined in the IDMC charter.

FL and MZL participants will be randomized separately, based on different stratification factors. The 3 stratification factors for participants with FL include POD24 (progression of disease within 24 months after initial diagnosis; yes vs no), refractoriness to prior anti-CD20 mAb therapy (yes vs no), and the number of prior lines of therapy ($< 2 \text{ vs} \ge 2$). The 1 stratification factor for participants with MZL is the number of prior lines of therapy ($< 2 \text{ vs} \ge 2$).

The primary analysis will be run when 174 PFS events are observed in the FL population. The timing of the analysis is independent of the recruitment target in the MZL population. The overall population analysis may be run concomitantly to the MZL population analysis.

Recruitment will be stopped when the required 528 participants with FL for the primary analysis and at least 60 participants with MZL have been randomized. The maximum number of randomized participants with MZL is 90.

An IRC will review PET and CT/MRI images to determine ORR, PFS, and DoR according to Lugano response criteria in the FL and overall populations. Details regarding the IRC constitution and procedures will be provided in a separate IRC charter.

Estimated Duration of Study Participation

The study duration for an individual participant is divided into the screening period (up to 28 days), treatment period (up to twelve 28-day cycles), and follow-up period (up to 60 months after EOT). The total duration may be up to approximately 6 years per participant.

Table 2: Key Study Design Elements (Continued)

IDMC	An IDMC will monitor data to ensure the safety of the participants enrolled in this study, and evaluate the efficacy of study treatment at a prespecified interim analysis for futility. Details regarding IDMC constitution, responsibilities, authorities, and procedures will be provided in a separate IDMC charter.
Coordinating Principal Investigator	University of British Columbia Vancouver, Canada

Treatment Groups and Duration:

Treatment Group A:

- Tafasitamab (12 mg/kg IV), 28-day cycle
 - Cycles 1 to 3: Days 1, 8, 15, and 22
 - Cycles 4 to 12: Days 1 and 15
- Rituximab (including biosimilars; 375 mg/m² IV), 28-day cycle
 - Cycle 1: Days 1, 8, 15, and 22
 - Cycles 2 to 5: Day 1
- Lenalidomide (including generics; 20 mg PO once daily), 28-day cycle
 - Cycles 1 to 12: Days 1 to 21

Treatment Group B:

- Tafasitamab placebo (0.9% saline solution) IV, 28-day cycle
 - Cycles 1 to 3: Days 1, 8, 15, and 22
 - Cycles 4 to 12: Days 1 and 15
- Rituximab (including biosimilars; 375 mg/m² IV), 28-day cycle
 - Cycle 1: Days 1, 8, 15, and 22
 - Cycles 2 to 5: Day 1
- Lenalidomide (including generics; 20 mg PO once daily), 28-day cycle
 - Cycles 1 to 12: Days 1 to 21

Note for both treatment groups:

- Tafasitamab/placebo
 - Every effort should be made to administer on Days 1, 8, 15, and 22 of Cycles 1 to 3 and then Days 1 and 15 for Cycles 4 to 12. If delays in infusion occur, the subsequent infusion date should not be changed (eg, if the tafasitamab/placebo infusion scheduled for C2D1 is delayed to C2D4 or later, this infusion should be skipped and the next infusion should be C2D8).

• Lenalidomide:

- For participants with moderate renal insufficiency (creatinine clearance ≥ 30 mL/min to < 60 mL/min), the starting dose of lenalidomide must be reduced to 10 mg QD on the same schedule. The dose of lenalidomide may be increased to 15 mg QD on Days 1 to 21 of each cycle if no Grade 3/4 lenalidomide-related toxicities occur after 2 cycles.
- Lenalidomide should be taken at approximately the same time every day.

• Rituximab:

[figure not shown]
Rituximab infusion should be administered at approximately 30 minutes after tafasitamab/placebo infusion but no less than 15 minutes after the tafasitamab/placebo infusion is completed (see Section 6.1); to avoid skipping a dose, rituximab infusion is allowable the next day.

The treatment period for each participant starts with first intake of study treatment at C1D1. All subsequent treatment days and assessments are calculated from C1D1. The timing of subsequent treatment days and assessments should not change and should remain on schedule, regardless of interruptions in study drug administration.

Adherence to the study design requirements, including those specified in the SoA, is essential and required for study conduct. Figure 1 presents the study design, and Table 3 and Table 4 present the schedule of activities and laboratory assessments, respectively.

See Section 6 for additional information on tafasitamab/placebo, lenalidomide, and rituximab administration.

Figure 1: Study Design Schema

^{*}Randomization will apply separately for FL versus MZL populations.

Table 3: Schedule of Activities

	Screening Period				Trea	atme	nt Pe	riod]	Follow-Up P	eriod	
				Cycle 1 da		C	ycles (± 1				ycle 4 days ^a)		Safety Follow-Up	Efficacy Follow-Up	Survival Follow-Up	
Activities	Up to Day -1	C1D1		Day 15	Day 22	Day 1	Day 8	Day 15	Day 22	Day 1		EOT (± 2 days)	90 Days From EOT (± 7 days)		Every 12 Weeks From EOT (± 4 weeks)	Notes
Administrative and go	eneral proce	dures ((see S	ectio	n 8.1)					•					
Informed consent	X															
Demography and medical history	X															
Inclusion/exclusion criteria	X	X														
Lenalidomide counseling	X	X				X				X		X				
Anticancer therapies and procedures	X												X	X	X	
IRT registration	X	X	X	X	X	X	X	X	X	X	X	X				
Treatment administra	tion (see Se	ction 6	.1)													
Tafasitamab/placebo		X	X	X	X	X	X	X	X	X	X					Up to 12 cycles.
Lenalidomide		X				X				X						Up to 12 cycles, Day 1 to Day 21.
Rituximab		X	X	X	X	X				X						Up to 5 cycles.
Safety assessments (se	e Section 8.	3)														
Concomitant medications	X	X	X	X	X	X	X	X	X	X	X	X	X			
Adverse events	X	X	X	X	X	X	X	X	X	X	X	X	X			
Physical examination	X*	X				X				X		X*				*Comprehensive examination at screening and EOT; targeted for all other visits.
B-symptoms	X	X				X				X		X				
ECOG performance status	X	X				X				X		X				
Vital signs	X	X	X	X	X	X	X	X	X	X	X	X				
Body weight	X	X				X				X		X				

Table 3: Schedule of Activities (Continued)

	Screening Period				Trea	atme	nt Pe	riod]	Follow-Up P	eriod	
				Cycle 1 day		C		2 and day ^a)			ycle 4 days ^a)		Safety Follow-Up	Efficacy Follow-Up	Survival Follow-Up	
Activities	Up to Day -1	C1D1		Day 15	Day 22	Day 1	Day 8	Day 15	Day 22	Day 1	Day 15	EOT (± 2 days)	90 Days From EOT (± 7 days)		Every 12 Weeks From EOT (± 4 weeks)	Notes
Safety assessments (co	ntinued; se	e Sectio	n 8.3)							•					
Height	X															
12-lead ECG	X															Repeat as clinically indicated after screening.
2D-ECHO or MUGA scan	X															
Efficacy assessments (s	see Section	8.2)														
Bone marrow core biopsy/bone marrow aspirate* (local)	X					X*						X‡				*If a biopsy is not clinically feasible. an aspirate should be collected. †At the time of radiologic CR only if bone marrow is involved at screening. ‡Only if bone marrow is involved at screening and morphologic CR is not seen on treatment.
Bone marrow aspirate for central MRD assessment	X					X	*					X				*At the time of radiologic CR only if bone marrow is involved at screening.
PET scan	X									X*		Х*,†		X*,†		*Only to confirm radiologic CR in FDG-avid participants. †Repeat only if no prior on-treatment PET was performed.
CT/MRI	X	Year 1 Years Years	2-3:	every	y 16 w	veeks	(4 m	$0, \pm 2$	wk)			X		X*		*Only if EOT is not due to disease progression.

Table 3: Schedule of Activities (Continued)

	Screening Period		Treatment Period]	Follow-Up P	eriod	
				Cycle 1 da							/cle 4 days ^a)		Safety Follow-Up	Efficacy Follow-Up	Survival Follow-Up	
Activities	Up to Day -1	C1D1		-	Day 22	Day 1	Day 8	Day 15	Day 22	Day 1		EOT (± 2 days)	90 Days From EOT (± 7 days)		Every 12 Weeks From EOT (± 4 weeks)	Notes
Efficacy assessments (c	•	L	 									(=, 2)	(', .,		(1	- 10000
Response assessment		Years	Year 1: every 12 weeks (3 mo, ± 2 wk) Years 2-3: every 16 weeks (4 mo, ± 2 wk) Years 4-6: every 24 weeks (6 mo, ± 3 wk)									X		X*	Χţ	
Survival status															X	
Quality-of-life assessm	ents (see Se	ection 8	3.2.5)													
EORTC QLQ-C30 questionnaire		X				X				X		X		X*		*During efficacy follow-up, questionnaires
EQ-5D-5L questionnaire		X	X X X									X		X*		must be completed at the same time as response
FACT-Lym questionnaire		X				X				X		X		X*		assessment (see above).

^a Additional visit windows will be provided in referenced sections, as appropriate.

Table 4: Schedule of Laboratory Assessments

	Screening				Tre	atmen	t Peri	od					Fo	llow-Up Per	riod	
		Cycle 1 (± 1 Day)											Safety Follow-Up	Efficacy Follow-Up	Survival Follow-Up	
Activities	Up to Day -1	C1D1	Day 8	Day 15	Day 22	Day 1	Day 8	Day 15	Day 22	Day 1	Day 15	ЕОТ	90 Days From EOT (±7 days)		Every 12 Weeks From EOT (± 4 weeks)	Notes
Laboratory assessm	ents (see Se	ction 8.	3.5)													
Hematology	X	X	X	X	X	X		X		X		X				
Clinical chemistry	X	X	X	X	X	X		X		X		X				
Coagulation	X	X				X				X		X				
C-reactive protein	X	X				X				X		X				
Urinalysis	X															Repeat if clinically indicated after screening.
Creatinine clearance	X															See Appendix C.
Hepatitis virus and HIV serology	X															
IgG, IgA, and IgM	X					X*				X*		X				*Cycle 2 and every 2 cycles
TSH	X					X*				X*		X				thereafter.
Pregnancy testing	X*	X*	X	X	X	X		Χ†		Χ†		X‡	X‡			*Serum at screening and Day 1 before first dose. †Repeat monthly or biweekly on treatment; see Section 8.3.5.2. ‡Repeat monthly between EOT and safety follow-up.

 Table 4:
 Schedule of Laboratory Assessments (Continued)

	Screening			Tre	atmen	t Peri	od					Fo	ollow-Up Per	riod	
			Cycle 1 1 Day		(2 and Day)	3		cle 4 Days)		Safety Follow-Up	Efficacy Follow-Up	Survival Follow-Up	
							,					90 Days		Every 12 Weeks	
Activities	Up to Day −1	C1D1	Day 15	Day 22	Day 1	Day 8	Day 15	Day 22	Day 1	Day 15	EOT	From EOT (±7 days)		From EOT (± 4 weeks)	Notes
	y											(1 2005/2)		(1 4 4	

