- Participants with negative PET scan at baseline should be followed using CT or MRI imaging. Additional PET scans may be performed at the treating investigator's discretion but are not required.
- Participants with a positive PET scan at baseline (FDG-avid lymphoma) who achieve radiologic CR during treatment should be assessed by PET scan within 4 weeks (± 2 weeks) of the CT/MRI scan, noting the CR to evaluate for metabolic response. Subsequent PET scans are not required if a confirmatory PET scan is performed during treatment; otherwise, a PET scan will need to be repeated at EOT.
- CT/MRI scans are to be performed according to the following schedule:
 - Year 1: Every 12 weeks (3 months, ± 2 weeks), including the EOT visit.
 Circumstances where scans cannot be performed at EOT (eg, due to hospitalization, hospice care, recent per-protocol scan, etc.) must be properly documented in the eCRF
 - Years 2 to 3: Every 16 weeks (4 months, \pm 2 weeks)
 - Years 4 to 6: Every 24 weeks (6 months, \pm 3 weeks)
- For CT/MRI scans reporting PD, a PET-CT or PET-MRI scan should be performed within 4 weeks (± 2 weeks) for confirmation of progression.

Response assessments using Lugano criteria (Cheson et al 2014) are to be performed each time lesions are assessed.

Participants who discontinue treatment for reasons other than disease progression will enter the efficacy follow-up period (see Section 8.9.2). Lesions must followed using the same modality and schedule as was used during the treatment period until progression of disease, initiation of new anticancer therapy, death, or withdrawal of consent.

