APPENDIX H. LUGANO RESPONSE CRITERIA FOR MALIGNANT LYMPHOMA

Target and Nontarget Lesions

Up to 6 of the largest target nodes, nodal masses, or other lymphomatous lesions that are measurable in 2 diameters should be identified from different body regions representative of the participant's overall disease burden and include mediastinal and retroperitoneal disease, if involved. At baseline, a measurable node must be > 15 mm in longest diameter (LDi). Measurable extranodal disease may be included in the 6 representative measured lesions. At baseline, measurable extranodal lesions should be > 10 mm LDi.

All other lesions (including nodal, extranodal, and assessable disease) should be followed as nonmeasured disease as nontarget lesions (eg, cutaneous, GI, bone, spleen, liver, kidneys, pleural or pericardial effusions, ascites, bone, BM).

Split Lesions and Confluent Lesions

Lesions may split or may become confluent over time. In the case of split lesions, the individual product of the perpendicular diameters (PPDs) of the nodes should be summed together to represent the PPD of the split lesion; this PPD is added to the sum of the PPDs of the remaining lesions to measure response. If subsequent growth of any or all of these discrete nodes occurs, the nadir of each individual node is used to determine progression. In the case of confluent lesions, the PPD of the confluent mass should be compared with the sum of the PPDs of the individual nodes, with more than 50% increase in PPD of the confluent mass compared with the sum of individual nodes necessary to indicate PD. The LDi and smallest diameter (SDi) are no longer needed to determine progression.

Response	Imaging	Lymph Node and Extra Lymphatic Sites	Nontarget Lesions	Liver and Spleen	Bone Marrow	New Lesion
CR	PET	Score of 1, 2 or 3 ^a with our without a residual mass on 5PS. ^b	Not applicable	Not applicable	No evidence of FDG-avid disease in marrow	None
	CT	Target nodes/nodal masses must regress to ≤ 1.5 cm in LDi. No extra lymphatic site of disease.	Absent	Regress to normal	Normal by morphology; if intermediate, IHC negative	None

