Rationale for change: Flexibility for determining eligibility with respect to certain procedures that cannot be practically repeated.

18. Section 8.1.4.2.1, Central Pathology Review

Description of change: Incorporated relevant text into Section 8.1.4.2.

Rationale for change: Clarification and elimination of redundancy.

19. Section 8.2.4, Radiographic and Metabolic Imaging Assessments

Description of change: Revised section to ensure proper radiologic and metabolic imaging will be performed at the correct timepoints: participants with FDG nonavid disease do not require repeat PET assessments, and participants with FDG-avid disease only require 1 subsequent PET scan (either at radiologic CR or at EOT). Clarified that the schedule of radiologic imaging is to be followed while on treatment and in efficacy follow-up.

Rationale for change: Clarification of procedural requirements and timepoints.

20. Section 8.3.5.4, Hepatitis Virus Serology

Description of change: Removed collection of HBV DNA titer after EOT.

Rationale for change: Removed unnecessary sample collection.

21. Section 8.8, End of Treatment and/or Early Treatment Discontinuation

Description of change: Clarified that the EOT visit is to occur on Cycle 12 Day 28 if the participant completes the prescribed study treatment regimen or at the time the decision is made to discontinue study treatment.

Rationale for change: To remove language related to the EOT visit occurring 90 days after the last dose because this interval only applies to the safety follow-up visit.

22. Section 8.9.1, Safety Follow-Up

Description of change: Clarified that the safety follow-up visit is to occur 90 days after EOT.

Rationale for change: Clarification of visit timings.

23. Section 8.9.2, Efficacy Follow-up

Description of change: Clarified that participants who discontinue treatment for reasons other than disease progression will continue to have disease assessments until progression of disease, start of new anticancer therapy, withdrawal of consent, lost to follow-up, or death.

Rationale for change: Clarification of visit timings.

24. Section 8.9.3, Survival Follow-up/Completion of Study

Description of change: Clarified the interval and window for performing survival follow-up assessments (every 12 weeks with a \pm 4-week window)

Rationale for change: Clarification of visit timings.

25. Section 8.10, Appropriateness of Measurements

Description of change: Removed section.

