7.3.2.1. Progression-Free Survival in the Overall Population

Progression-free survival by INV assessment in the overall population (FL and MZL) will be compared and analyzed in the same manner as described in Section 7.3 for the PFS in the FL population. The strata information for the stratified log-rank test will be based on the randomization factor used for both cohorts, FL and MZL: number of prior lines of therapy ($< 2 \text{ versus} \ge 2$).

The p-value obtained from the stratified log-rank test for PFS in the overall population, using the strata information based on IRT that was used for randomization, as well as stratification by FL versus MZL, will be used for hierarchical testing.

As mentioned in Section 7.3, participants with different initial diagnosis by INV and in the IRT will be considered as mentioned in the eCRF.

7.3.2.2. Positron-Emission Tomography-Complete Response Rate in the FDG-Avid Follicular Lymphoma Population

The PET-CR rate is defined as the proportion of FDG-avid participants who achieved a CR as per Lugano classification (Cheson et al 2014) with a PET-negative result defined as a complete metabolic response at any time after start of treatment over the FDG-avid FL population at baseline. FDG-avid FL participants with no postbaseline assessment by PET or those who did not achieve a PET-CR will be classified as "non-CR-responder."

The CR rate will be compared between the 2 treatments groups using a stratified CMH test. The odds ratio and its 95% CIs calculated from the stratified CMH test will also be presented. The number of participants classified as PET-CR responders and the respective rates as well as 95% CIs (using Clopper-Pearson) will be presented.

Analysis of the key secondary endpoint of PET-CR will be performed for participants with FDG-avid FL in the FAS. If the null hypothesis is rejected at a 2-sided significance level of 5%, this key secondary endpoint is met. The p-value obtained from the CMH test for PET-CR rate by INV assessment in the FDG-avid FL population, using the strata information based on IRT that was used for randomization, will be used for hierarchical testing.

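### Protocol Table 3 and Section 8.2.4 disagree on which FDG-avid participants have an end-of-treatment PET, and a participant without a postbaseline PET is scored a PET-CR failure

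*Protocol*

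**What the plan says.** **Table 3 (Protocol Section 1).** The PET cells at EOT and in efficacy follow-up carry two marks, an asterisk and a dagger. The asterisk note, followed by the dagger note, reads "Only to confirm radiologic CR in FDG-avid participants. †Repeat only if no prior on-treatment PET was performed". Nothing says that either mark alone is enough.

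**Protocol Section 8.2.4.** Participants with a positive baseline PET "who achieve radiologic CR during treatment should be assessed by PET scan within 4 weeks" (± 2 weeks). No further PET is required once a confirmatory scan has been done on treatment; "otherwise, a PET scan will need to be repeated at EOT".

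**Amendment 7 summary, item 19.** It describes the revised Section 8.2.4 as meaning that "participants with FDG-avid disease only require 1 subsequent PET scan (either at radiologic CR or at EOT"). I cite this only for intent.

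**Appendix H.** CR by PET is a score of 1, 2 or 3 "with our without a residual mass on 5PS". CR by CT requires target nodes to shrink to 1.5 cm or less in longest diameter.

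**Endpoint and scoring.** The key secondary endpoint is a complete metabolic response reached at any point once treatment has begun, in FDG-avid FL (Protocol Table 5). SAP 7.3.2.2 keeps everyone in the denominator: "FDG-avid FL participants with no postbaseline assessment by PET or those who did not achieve a PET-CR will be classified as" non-responders. Protocol 10.4.1.2.2 has the same rule.

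**The concern.** The scan that measures the endpoint appears to be conditional on a different outcome. Consider an FDG-avid participant whose nodes have shrunk at the end of Cycle 12 but still exceed 1.5 cm. That is not a CT CR, yet Appendix H allows it to be a metabolic CR. Under Table 3 no EOT PET is due, and the participant is scored a failure without being assessed. Under the broad reading of Section 8.2.4 the same participant is scanned and may be a responder.

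At sites working from Table 3, the endpoint becomes CT CR that is also PET-negative, which is narrower than the one defined. The observed rate then depends partly on which passage each site followed. PET-CR is second of the three key secondary endpoints in the fixed sequence (Protocol 10.3), so failing to reject it ends formal testing before overall survival.

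**Working it through.** **1. The passages side by side.** For an FDG-avid participant with no PET since baseline:

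| CT status at EOT | Table 3 | 8.2.4, broad reading | 8.2.4, narrow reading |
|---|---|---|---|
| CT CR | PET | PET | PET |
| No CT CR | No PET scheduled | PET | No PET scheduled |

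The closing clause of Section 8.2.4 states no CT condition of its own, which favours the broad reading. It sits in a bullet about participants who reach radiologic CR, which allows the narrow one. The Amendment 7 description, one PET at radiologic CR or at EOT, fits the broad reading.

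**2. Safeguards in the SAP.** SAP 7.4.2 summarises reasons for missing MRD assessments; there is no counterpart for PET. For PET-CR, SAP 7.6 offers Fisher's exact test and eCRF strata, and neither addresses unscanned participants.

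**3. Illustrative size.** The plan states no PET-CR rate, power or sample size, so there is no figure to reproduce.

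Inputs:
- n = 264 per arm: 528 FL participants randomized 1:1. This is an upper limit, because it treats every FL participant as FDG-avid.
- Two-sided 5% test (Protocol 10.4.1.2.2).
- Assumed: true metabolic CR of 52% versus 40%.
- Assumed: the same share f of metabolic CRs is never scanned in both arms.

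Observed rate = true rate × (1 − f). Power = Φ(d/SE − 1.96), where d is the observed difference and SE = √[(p1(1−p1) + p0(1−p0))/n].

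- f = 0: SE = √[(0.52×0.48 + 0.40×0.60)/264] = 0.0431; 0.12/0.0431 − 1.96 = 0.83; power 80%.
- f = 0.4: SE = √[(0.312×0.688 + 0.24×0.76)/264] = 0.0388; 0.072/0.0388 − 1.96 = −0.10; power 46%.

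| f | Observed rates, 52 vs 40 | Difference (points) | Power, 52 vs 40 | Power, 55 vs 40 |
|---|---|---|---|---|
| 0 | 52.0 / 40.0 | 12.0 | 80% | 93% |
| 10% | 46.8 / 36.0 | 10.8 | 72% | 88% |
| 20% | 41.6 / 32.0 | 9.6 | 63% | 81% |
| 30% | 36.4 / 28.0 | 8.4 | 55% | 73% |
| 40% | 31.2 / 24.0 | 7.2 | 46% | 63% |

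The last column assumes 55% versus 40% and uses the pooled variance under the null, which changes power by less than half a point. With 224 per arm, that column runs from 89% to 56%.

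f is the share unscanned across the whole trial. If 40% of metabolic CRs have a CT residual mass but only half of them are at sites following Table 3, f = 0.40 × 0.50 = 20%.

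**4. Unequal loss.** If the unscanned share differed by arm, the bias could go either way. With equal true rates of 45% and shares of 10% and 30%, the observed rates are 0.45×0.90 = 40.5% and 0.45×0.70 = 31.5%.

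**The case against.** A reader of Table 3 alone might infer that the plan leaves FDG-avid participants with a residual mass without any PET. The documents do not support that. The efficacy heading in Table 3 points to Section 8.2, and Section 8.2.4 calls for an EOT scan when none was done on treatment. On that reading an unscanned participant is a site deviation, not the plan. On the narrow reading, Section 8.2.4 agrees with Table 3 and there is no conflict between them. Both points are fair, but they show that the rule is unsettled. The broad reading leaves Table 3 wrong, and the narrow one leaves the endpoint unmeasured in part of its own population.

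Nor is an unscanned participant necessarily unscanned for good. The follow-up cell permits a PET if CT CR comes later, Section 8.2.4 asks for one when CT or MRI shows progression, and investigators may order extra imaging. This stands, and it lowers f. It does not give a systematic assessment to someone in stable partial response by CT.

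The power figures rest on assumed rates, and the 52% versus 40% case starts at about 80% power by construction. That also stands; they show direction and rough scale only. Equal loss costs power and does not create a false positive. Nothing in the documents indicates unequal loss in this double-blind trial.

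Finally, the reading rests on footnote marks in a table extracted from PDF, and the adjoining bone marrow row has a dagger note with no matching cell. The PET row shows both marks in both cells, so I treat it as reliable.

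**Conclusion.** The point holds as an inconsistency between two current passages. Table 3 limits the EOT PET to confirming a radiologic CR; Section 8.2.4, most naturally and in line with its stated intent, does not. The Protocol Summary makes adherence to the schedule of activities essential, so some sites can be expected to follow Table 3. Those sites would enter unassessed participants as failures on an alpha-controlled endpoint that gates overall survival.

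The documents do not show that residual-mass participants go unscanned throughout the trial, that a tafasitamab benefit would be hidden, or that the comparison is biased toward either arm. The loss of power cannot be derived from them. The fall from about 80% to between 72% and 46% requires 52% versus 40% true rates, 264 FDG-avid participants per arm, and 10% to 40% of metabolic CRs never scanned, equally in both arms. This should be corrected; it does not touch the primary analysis.

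**What to change.** - **Table 3:** remove the asterisk from the EOT PET cell and keep the dagger, so that an FDG-avid participant with no on-treatment PET has one at EOT whatever the CT response.
- **Section 8.2.4:** state that the closing clause covers FDG-avid participants without radiologic CR.
- **SAP:** add a table, by arm, of the number of FDG-avid participants with no postbaseline PET, with their CT response. This also covers participants already past EOT, whose scans cannot be recovered.
- **Scanned participants only:** keep any such summary descriptive. Being scanned depends on response after randomization, so it is not a fair comparison of metabolic CR rates.

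The cost is a wording clarification and one extra table. Some sites will do EOT PETs that they would have skipped, but these are scans that the stated intent of Section 8.2.4 already calls for.
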